### **3.10 Steering Committee**

A protocol Steering Committee will be appointed to periodically review safety reports from the study, as well as the reports from the two independent clinical adjudication committees. The Steering Committee will evaluate these reports and provide assessments to the Savient Senior Management, including the Savient Chief Medical Officer.

## **4 PROTOCOL AMENDMENTS, OTHER CHANGES IN STUDY CONDUCT**

### **4.1 Protocol Amendments**

Any changes to the protocol will be made in the form of an amendment. Unless the changes are designed to eliminate an apparent immediate hazard to patients, both Savient and the governing IRB must grant approval of the amendment before any changes may be implemented in study conduct.

### **4.2 Other Changes in Study Conduct**

Changes in study conduct are not permitted. Any unforeseen changes in study conduct will be recorded in the clinical study report.

## **5 DATA MANAGEMENT**

### **5.1 Data Collection**

Investigators or their designees will enter study data in the CRFs/eCRFs and ensure the data is accurate and complete and that all entries are verifiable with source documents. Study monitors will review data in the CRFs/eCRFs for completeness and accuracy, and instruct site personnel to make any required corrections or additions in a manner compliant with Good Clinical Practice (GCP) guidelines.

### **5.2 Database Management and Quality Control**

Information entered into the database is subjected to systematic logic and consistency checking routines. Obvious errors will be corrected by the appropriate data management personnel in accordance with the data handling and entry guidelines for the study. Findings from the process are reviewed by qualified Data Management or Clinical personnel, after which query forms are returned to the investigational site for resolution of key variables. Each site is expected to respond promptly to data queries. All queries related to AEs must be signed by an investigator. Periodic quality control edit checks of key safety and efficacy data in the database will be made throughout the duration of the study.

Concomitant medications entered into the database will be coded using the World Health Organization Drug Dictionary which classifies according to therapeutic/pharmacological class. Coexistent diseases and AEs will be coded using the Medical Dictionary for Regulatory Activities (MedDRA).

When the database has been declared to be complete and accurate, the database will be locked. Any changes to the database after that time can only be made by joint written agreement between the Savient Clinical, Statistical and Data Management Directors.

## **6 STATISTICAL METHODS**

### **6.1 Statistical Methods**

The statistical analysis will be coordinated by the responsible biostatistician. The Statistical Analysis Plan (SAP) will provide additional details on the planned statistical analysis. The SAP will be finalized before the database is locked. Any deviations from the SAP will be described in the clinical study report.

Descriptive statistics (number of patients, mean, standard deviation [SD], minimum, median, and maximum) will be used to summarize continuous variables. Descriptive statistics for categorical variables will consist of frequency and percentage.

#### **6.1.1 Population**

The analyses will be performed on the Intent-to-Treat (ITT) population. The ITT population will be comprised of all enrolled patients who received at least 1 dose of KRYSTEXXA and have some follow-up data.

#### **6.1.2 Background and Demographic Characteristics**

Demographics and other baseline characteristics will be summarized for the ITT population using standard descriptive statistics (number of patients, mean and standard deviation, minimum, median, and maximum), which will be reported and updated for all baseline variables at each data review. All categorical/qualitative data will be presented using absolute and relative frequency counts and percentages. The total number of subjects in the treatment group overall (N) will be used as the denominator for percentage calculations, unless stated otherwise in the SAP. The prediction and profile of the patient's accrual will be made at each review.

#### **6.1.3 Study Medication**

Summary statistics for the total exposure to KRYSTEXXA during the treatment period (number of KRYSTEXXA infusions) will be tabulated.

#### **6.1.4 Concomitant Therapy**

Concomitant medications will be summarized by therapeutic/pharmacological class. In addition, they will be listed by treatment group, name of drug, dates administered and indication.

#### **6.1.5 Efficacy Evaluation**

One efficacy endpoint in this study is normalization of SUA to < 6 mg/dL. Descriptive statistics will be employed to summarize the proportion of responders, where a responder is defined as a patient whose SUA values were < 6 mg/dL at their final 2 consecutive study visits. Summary statistics will be provided for the number of swollen joints and tender joints at baseline, 6 months

(Visit 13) and 12 months (Visit 26) or Early Discontinuation; for changes in numbers of gout flares based on patient reported history at 6-week intervals for Months 1-3 and 3-month intervals thereafter; and for elimination of tophi, i.e., the number of patients with a reported tophus resolution at 6 months (Visit 13) and 12 months (Visit 26) or Early Discontinuation.

It is anticipated that there may be a considerable number of study patients who will drop out of the study. The sponsor will make every effort to identify the reason(s) for dropout before reaching the primary safety endpoint. For the analysis of each efficacy endpoint, various sensitivity analyses will be performed under different assumptions of potentially informative dropouts. For example, in the responder analysis, one analysis will be based on the ITT population with various imputation methods for missing values at the end. Analyses will also be performed assuming all “informative” dropouts are non-responders. For continuous efficacy variables, sensitivity analyses will be performed using standard mixed-effect model repeated measure (MMRM) methods. All the analyses will be summarized using 95% confidence interval estimates. The resulting summarized statistics for efficacy will be compared to those reported from the pre-approval Phase 3 studies.

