## PROTOCOL SYNOPSIS

Name of product	KRYSTEXXA® (pegloticase)
Drug substance:	Pegloticase is a uric acid-specific enzyme which is a polyethylene-glycol conjugated (PEGylated) product that consists of recombinant, modified, mammalian urate oxidase (uricase) produced by a genetically modified strain of Escherichia coli . Uricase is covalently conjugated to monomethoxypoly(ethylene glycol) (mPEG; 10 kDa molecular weight). The cDNA coding for uricase is based on mammalian sequences. Each uricase subunit has a molecular weight of approximately 34 kilodaltons (kDa). The average molecular weight of pegloticase (tetrameric enzyme conjugated to a mean of 10.2 mPEG molecules) is approximately 540 kDa.
Protocol number:	M0401
Study title:	Observational study of the use of KRYSTEXXA® (pegloticase) in adult hyperuricemic patients with gout refractory to conventional therapy
Phase:	4
Objectives:	
Primary:
 
To evaluate the frequency and severity of infusion reactions (IRs), anaphylaxis, and immune complex-related events.
 
Secondary:
 
To identify serious adverse events (SAEs) associated with KRYSTEXXA therapy.
 
To further evaluate the efficacy of KRYSTEXXA in this patient population of adult hyperuricemic patients with gout refractory to conventional therapy.

Study design:	This is a multicenter, open-label, single-arm observational study.
Investigational plan:	Approximately 1500 patients will be enrolled in order to observe treatment of up to 500 patients for a duration of 1 year. Patients who discontinue treatment before 51 weeks will be asked to remain in the study for follow-up assessments for the remainder of their planned treatment duration. The number of patients to be enrolled will be reassessed approximately 2 years after the first patient is enrolled. The study will be conducted at approximately 300 centers in the United States (US). It is estimated that approximately 2.5 years will be required for recruitment, from the first to the last patient's screening visit.

---

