Treatment:	Patients eligible for initial treatment with KRYSTEXXA 8 mg by intravenous (i.v.) infusion every 2 weeks will be offered enrollment into the observational study for a year. Serum uric acid (SUA) levels will be monitored prior to infusion and therapy will be discontinued if levels increase above 6 mg/dL on two consecutive measurements. If the SUA is noted to be above 6 mg/dL the sponsor suggests that a repeat SUA should be drawn when the result is noted to confirm, and if the 2 consecutive levels are noted to be above 6 mg/dL then it is advised to discontinue therapy.
Study duration:	Approximately 63 weeks, including 51 weeks of treatment and 12 weeks of follow-up.
• Selection criteria	
Inclusion criteria:
 

• Adult patients (age <math>\geq</math> 18 years) with chronic gout refractory to conventional therapy, defined as patients who have failed to normalize SUA and whose signs and symptoms are inadequately controlled with xanthine oxidase inhibitors at the maximum medically appropriate dose, or for whom these drugs are contraindicated.

• Patients who have made the decision, along with their treating physician, to begin treatment with KRYSTEXXA.

• Patients who are willing and able to give informed consent and adhere to visit/protocol schedules (informed consent must be given before the first study procedure is performed).

 
Exclusion criteria:
 

• Glucose-6-phosphate dehydrogenase (G6PD) deficiency

• Non-compensated congestive heart failure

• Pregnancy or breast feeding

• Prior treatment with pegloticase or another recombinant uricase

• Known allergy to urate oxidase

• Prior treatment or concomitant therapy with a polyethylene glycol (PEG)-conjugated drug

• Recipient of an investigational drug within 4 weeks prior to study drug administration or plans to take an investigational agent during the study

Investigational drug:	None
Reference therapy:	KRYSTEXXA® (pegloticase) 8 mg i.v. every 2 weeks

---

Efficacy criteria:	Normalization of SUA to < 6 mg/dL  Decrease in the number of swollen joints and the number of tender joints  Decrease in the frequency of gout flares  Reduction in the number of tophi

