Safety criteria:	IRs, anaphylaxis, and immune complex-related adverse events, serious adverse events and adverse event profile, including gout flares
Statistical methods:	
Descriptive statistics will be employed to summarize the proportion of responders, where a responder is defined as a patient whose SUA values were < 6 mg/dL at their final 2 consecutive study visits. Descriptive statistics will be provided for the number of swollen joints and tender joints at baseline, 6 months and 12 months or Early Discontinuation; for changes in numbers of gout flares based on patient reported history at 6-week intervals for Months 1-3 and 3-month intervals thereafter; and for change in the number of tophi at 6 months (Visit 13) and 12 months (Visit 26) or Early Discontinuation.
 
It is anticipated that there may be a considerable number of study patients who will drop out of the study. The sponsor will make every effort to identify the reason(s) for dropout before reaching the primary safety endpoint. For the analysis of each efficacy endpoint, various sensitivity analyses will be performed under different assumptions of potentially informative dropouts. For continuous efficacy variables, sensitivity analyses will be performed using standard mixed-effect model repeated measure (MMRM) methods. All the analyses will be summarized using 95% confidence interval estimates. The resulting summarized statistics for efficacy will be compared to those reported from the pre-approval phase 3 studies.
 
Adverse events will be summarized by presenting the proportion of patients having any adverse event (AE), overall and by body system, and by event as defined by the Medical Dictionary for Regulatory Activities (MedDRA) preferred term. Separate summary tables will be provided for IRs, anaphylaxis AEs, and immune complex-related AEs.
 
For each type of the primary safety endpoints, one event, at most, will be counted per patient. The 95% (exact) confidence interval estimates for each type of safety endpoint will be reported for the rate of incidence both at the administrative interim analysis, for evaluating the feasibility of the study, and at the final analysis. The following hypothesis will be specifically tested: the rate of IRs seen in the phase 3 studies will be reduced in this study by monitoring SUA prior to infusions and

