#### **6.1.6 Safety Evaluation**

Adverse events will be summarized by presenting the proportion of patients having any AE, overall and by body system, and by event as defined by the MedDRA preferred term. Separate summary tables will be provided for IRs, anaphylaxis AEs, and immune complex-related AEs.

For each type of the primary safety endpoints, one event, at most, will be counted per patient. The 95% (exact) confidence interval estimates for each type of safety endpoint will be reported for the rate of incidence at the final analysis. The following hypothesis will be specifically tested: the rate of IRs seen in the Phase 3 studies will be reduced in this study by monitoring SUA prior to infusions and discontinuing therapy if levels increase to above 6 mg/dL, particularly when 2 consecutive levels above 6 mg/dL are observed. With at least 500 patients enrolled with 1 year follow-up, the power of detecting a 26% IR rate (the observed value from the pre-approval Phase 3 studies) against 13% is at least 90%. The rate of IRs reported during the study will be reported and compared descriptively to the rates observed in the pre-approval Phase 3 studies.

Descriptive statistics for laboratory values, vital signs, and their changes from baseline will be provided. Safety data will be listed as appropriate. Further details will be specified in the SAP.

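### Joint counts are planned as visit-by-visit summaries with no within-patient change, although the criterion is a decrease and the visits may describe different patients

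*Protocol*

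**What the plan says.** The Protocol Synopsis lists this efficacy criterion: "Decrease in the number of swollen joints and the number of tender joints". The analysis in Protocol section 6.1.5 reads "Summary statistics will be provided for the number of swollen joints and tender joints at baseline, 6 months" and continues "Visit 13) and 12 months (Visit 26) or Early Discontinuation; for changes in numbers of gout flares". The Synopsis statistical methods agree: "Descriptive statistics will be provided for the number of swollen joints and tender joints at baseline, 6 months and 12 months or Early Discontinuation". Neither place names a change for joints.

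Other measures are worded differently. Flares are given as changes in both places. For tophi the Synopsis has "for change in the number of tophi at 6 months (Visit 13", while section 6.1.5 counts patients with resolution. Section 6.1.6 has "Descriptive statistics for laboratory values, vital signs, and their changes from baseline will be provided".

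Joints are counted at screening (3.5.1), at Visits 13 and 26 (3.5.2.2), and once 4 weeks after the final infusion in patients who stop treatment (3.5.3) or leave the study (3.5.4). The later follow-up visits include no joint count (3.5.3, additional follow-up; Appendix 3, second schedule).

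On retention, the Synopsis says "Approximately 1500 patients will be enrolled in order to observe treatment of up to 500 patients for a duration of 1 year", and section 6.1.5 says "It is anticipated that there may be a considerable number of study patients who will drop out of the study". For each efficacy endpoint, section 6.1.5 promises sensitivity analyses under different informative-dropout assumptions, and MMRM for continuous variables. It does not give the MMRM response variable. It also promises 95% confidence intervals and a comparison with the Phase 3 studies. The SAP has no joint analysis, and its Tables section refers to 24-week completers without mentioning joints.

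**The concern.** A decrease is a statement about the same patients at two times. Summaries by visit show it only if the same patients are in each column, or if those missing resemble those present. Neither can be assumed here. At most about one third are planned to be on drug at one year, and section 3.5.2.1 ties stopping to SUA, so staying on drug is not random.

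If leavers start with more affected joints than stayers, the later column falls with no patient improving. If they start with fewer, a real decrease is hidden. The result would then be set beside the Phase 3 figures.

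The Early Discontinuation count could reduce the problem, but its role is open. On a natural reading it belongs to the 12-month time point. If pooled there, the column mixes week-51 counts with counts taken 4 weeks after a last infusion at any point in the year. If shown apart, the 12-month column holds only patients who reached Visit 26.

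**Working it through.** The documents give no joint mean, SD, expected decrease or power for joints, so there is no planned figure to reproduce. The calculation asks how large a false decrease the visit columns can show when nobody changes.

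**Inputs**
- From the Synopsis: retention to one year r = 500/1500 = 33.3%. This is an upper figure, since the plan says up to 500.
- Assumed: baseline mean of 8 joints in stayers and 12 in leavers.
- Assumed: share a of stoppers whose Early Discontinuation count is pooled into the later column, from 0 to 1.

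**Step 1: baseline column.** (500×8 + 1000×12)/1500 = 16000/1500 = 10.67.

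**Step 2: later column, zero true change.** Mean = (500×8 + a×1000×12)/(500 + a×1000).

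| a | Later mean | Apparent decrease from 10.67 |
|---|---|---|
| 0 | 4000/500 = 8.00 | 25% |
| 0.5 | 10000/1000 = 10.00 | 6% |
| 0.8 | 13600/1300 = 10.46 | 2% |
| 1 | 16000/1500 = 10.67 | 0% |

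**Step 3: the same in SD units.** The false decrease is (w − r)×D, where w = r/(r + a(1 − r)) is the stayers' share of the later column and D is the leavers' baseline mean minus the stayers'. At a = 0, 0.5, 0.8 and 1, w − r is 0.667, 0.167, 0.051 and 0.
- D = 0.25 SD: 0.17, 0.04, 0.01 and 0 SD.
- D = 0.5 SD: 0.33, 0.08, 0.03 and 0 SD.
- D = 1 SD: 0.67, 0.17, 0.05 and 0 SD.

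If D is negative, the sign reverses and a real decrease is hidden.

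**Step 4: the 6-month column.** One third is a one-year figure, and the documents give no 6-month retention. If 38% to 47% remained (an assumption that borrows the Phase 3 urate-response range in section 1.2.1), the baseline mean is 12 − 4r, or 10.48 to 10.12. With no stopper's count included, the false decrease is 2.48/10.48 = 24% to 2.12/10.12 = 21%.

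**Step 5: what pairing cures.** A simulation with zero true change, one third retained and selection on baseline severity (D = 0.73 SD) gave a false decrease of 0.48 SD from visit means and 0.00 from within-patient change.

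**Step 6: what pairing does not cure.** Assume 42% of patients respond with a change of −1 SD, the rest have 0, and only responders stay on drug. The true mean change is −0.42 SD. In patients still on drug, visit means and within-patient change both give −1.00 SD. Stoppers as a group average −(0.42 − 0.333)/0.667 = −0.13 SD. Pooling 50% of their counts gives −(0.333 + 0.333×0.13)/0.667 = −0.56. Pooling 80% gives −0.46, and 100% gives −0.42. The results are the same with or without change scores.

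**The case against.** The plan is not silent about patients who stop. The sentence in section 6.1.5 goes on to Early Discontinuation, and sections 3.5.3 and 3.5.4 collect a joint count at that visit. A reader might infer that stoppers are absent from the joint summaries, but the text does not say so. What is undefined is how their count is used. If most attend and are pooled, the distortion from baseline case mix is small.

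Section 6.1.5 also anticipates the dropout problem with informative-dropout analyses and MMRM, and section 6.1 puts the number of patients among the descriptive statistics, so shrinking denominators would be visible. This stands in part. These are sensitivity analyses, and nothing says whether MMRM would model the count or its change, or whether it would use the discontinuation count. The main description remains the visit columns.

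A reader might also infer that the plan ignores within-patient correlation and so loses precision. The documents do not support that: no unpaired test of joint counts is planned, and MMRM models the correlation.

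Finally, this is a descriptive secondary outcome in a single-arm safety study. That limits the weight of the point. It also makes the choice of MMRM as main estimate a trade-off rather than a correction.

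**Conclusion.** The gap is real and worth closing. The criterion is a decrease, but the planned summaries for joints do not measure change within patients, and the SAP does not supply it. The primary safety objective is not affected.

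Under the assumed means of 8 and 12 with one third retained, the false decrease runs from 25% down to 0%. Where it falls depends on how complete the Early Discontinuation counts are and whether they are pooled, which the plan does not fix. The 25% is the worst case under these assumptions, not an expected value. The joint means, the difference between stayers and leavers, and the attendance rates are all assumptions.

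A reader might infer that change scores would turn the joint result into a treatment effect. They would not. Pairing removes baseline case-mix differences. Change among patients still on drug remains conditional on staying on treatment (−1.00 against a true −0.42 SD in the illustration), and with no control arm no version isolates a treatment effect.

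**What to change.** In the Synopsis, section 6.1.5 and the SAP:

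1. Report within-patient change from baseline in swollen and, separately, in tender joint count, with 95% CI and n, at Visit 13, at Visit 26 and at Early Discontinuation. Beside each, print those same patients' baseline mean and the overall baseline mean.
2. Also report change to the last available count (Visit 26 or Early Discontinuation) in all treated patients with a baseline and any later count. This settles how the Early Discontinuation count enters.
3. Use change from baseline, adjusted for baseline count, as the response in the planned MMRM. It can stay a sensitivity analysis.
4. State with the results that on-drug change at a visit is conditional on remaining on treatment, that pairing does not remove response-driven selection, and that without a control arm the change does not isolate a treatment effect.

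The cost is wording, modest programming and a few more table rows. The counts used are already scheduled. The reported decrease may look smaller. The change cannot supply 6- or 12-month counts for patients who stopped before those visits, because none are scheduled.
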